3.1 Performance among participating clinics post-implementation

The Pathway Platform will be implemented in up to 20 primary care sites within the Advocate Aurora Health system and enroll a total of 200 patients for six-month duration. The visit where the patient has been onboarded to the Pathway Platform will be the enrollment visit (Figure 1). During the post- implementation period, data on patient outcomes will be collected through the Pathway Platform. At the end of the study an electronic and manual chart review for patients using the Pathway Platform will be conducted among participating clinics and performance related to measurement-based care, shared decision making and collaborative care, where applicable, will be assessed over the post-implementation period.

3.2 Retrospective Assessment: pre-implementation performance at the clinic level (before Pathway Platform implementation)

To assess Advocate's primary care sites performance pre-implementation, an electronic and manual chart review will be conducted from the same Advocate primary care clinics participating in the implementation study. Patients with a clinic visit at least 6 months prior to implementation (index visit) of the Pathway Platform and meeting the inclusion criteria for enrollment in the study, will be included in this analysis (figure 1). Patient history will be evaluated for three months prior to index visit to confirm eligibility. The goal is to capture patients with a new start, dose adjustment or switch of an antidepressant medication 6 months prior to the implementation index date (three-month inclusion window for patient identification). Six months of patient history will be “retrospectively” collected for this baseline patient cohort to assess the primary outcome, defined as PHQ-9 utilization, and other secondary outcomes outlined in the protocol. This analysis will serve as the comparison control for the primary and secondary outcomes to compare performance at the same clinics pre and post-implementation of the Pathway Platform. Depending on the number of eligible patients identified per site (20 per site), group level matching for age and sex may be conducted. The primary endpoint will be the proportion of patients with at least 2 PHQ-9 scores.

Figure 1: Study schematic

* Primary and secondary outcomes will be evaluated at 6 months, data collected beyond 6 months will be used for exploratory analysis

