4. SELECTION AND ENROLLMENT OF PARTICIPANTS

Patients will be recruited from up to 20 primary care clinics within Advocate Aurora Health that have agreed to implement the Pathway Platform. We aim to identify clinics that are representative of different geographic locations, patient populations, and care models for depression management, including behavioral health integration models. We will balance clinic diversity with feasibility to conduct this study. For example, we will only include clinics that have integrated Epic within their workflow so that the care team can easily access data collected from the patient in the Pathway Platform. We will also focus on clinics that have a large volume of patients diagnosed with depression as well as clinics that have care team members that are interested and engaged in depression care.

All care team members who care for patients with depression will be invited to participate in this implementation study and will have access to an online educational resource center. Patients fulfilling the following criteria will be eligible to download and use the Pathway Platform:

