4.3 Study Enrollment Procedures

This is a real-world implementation study with minimal interaction between the study team and patients. To address recent virtual visits in primary care due to COVID-19 and for the safety of the study team, study methods were developed to adapt virtual patient recruitment and e-consent during existing virtual visit processes. An in person consenting process is also available for in person clinic visits, when safe and appropriate, and will be supported by a study team member present at recruiting clinics.

Study team will review clinic schedules routinely for visits scheduled the next day and will flag potentially eligible patients and will discuss the list with the health care team. These patients will be introduced to the study opportunity by care team members during routine clinic visits.

- Consenting in person: If the patient is interested, they will be roomed with a study team member who will confirm study eligibility and provide written informed consent. If the patient is eligible and provides consent, the study team will share a secure message with a link for the Pathway App with the patient and the patient will be able to activate the Pathway App and start entering data. The secure message will be shared with the patient via AAH's secure patient portal. Or through an email for patients who have not activated their portal. The invitation message in the email will include an individualized link to download the App with a unique code specific to that patient to ensure security.

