4.4.3 Educational Scaffolding

An online Educational training program was developed using evidence-based medicine building

on measurement-based care and shared-decision making concepts as they relate to depression management. Educational material describes how the Pathway Platform can help care team members in clinical processes related to these process improvement measures. In clinics using a collaborative care model additional education material specific to this care model is provided. Educational material housed in an online resource center which includes reading material, presentations, and videos. Additionally, up to three audit and feedback sessions will be conducted for each participating clinic. The objectives of audit and feedback sessions are to benchmark performance measures, including shared decision making, reflect on current clinical practice and improvement strategies, and setting team-based action plans. Care team members who manage depression must complete specific training before they are able to enroll patients and begin using the Pathway Platform.

A training manual was also developed for patients. The manual describes the Pathway Platform functionality, as well as, how to use and interpret the data collected.

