8.2 Sample size and randomization

The primary outcome for this study is PHQ-9 utilization. Assuming 75% PHQ-9 utilization prior to implementation of the Pathway Platform and 90% PHQ-9 utilization after implementation of the Pathway Platform, we will need 100 patients per group, for a total of 200 patients, assuming 80% power and a 2-sided alpha of 0.05 using Pearson chi square test for two independent proportions. To allow for subgroup analyses the sample will include 200 patients per group, for a total of 400 patients; 200 patients will comprise the “post-implementation” cohort and 200 will comprise the “pre-implementation” cohort. **Table 2** presents additional sample size calculations based on different assumptions of PHQ-9 utilization.

Table 2: Sample size calculations based on different assumptions of PHQ-9 utilization, alpha = 0.05, Power = 80%.
--

PHQ-9 utilization pre-implementation	PHQ-9 in Pathway post-implementation	N patients per group
75%	80%	1,094 per group
75%	90%	100 per group
75%	95%	49 per group
50%	65%	170 per group
50%	80%	30 per group
50%	90%	20 per group

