8.3 Outcomes

8.3.1 Primary outcome

The primary process outcome is PHQ-9 utilization over a six-month period. For purposes of this study, PHQ-9 utilization will be defined as documentation of at least 2 PHQ-9 scores in the EMR over the initial 6-month study period. The proportion of patients who meet this definition will be compared between patients attending clinics pre- and post- implementation of the Pathway Platform. Additional analyses exploring the number of PHQ-9s over the study period will also be conducted.

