8.4 Data analysis

For primary and secondary hypothesis testing, process measures, patient clinical outcomes, and health care resource utilization will be compared pre- and post- implementation of the Pathway Platform.

Additional patient reported outcomes will be compared among patients using the Pathway Platform only at baseline and end of study. For pre-implementation, outcomes will be assessed among patients who visited one of the study clinics at least once over the pre-implementation study period and were eligible to use the Pathway Platform, if it had been available. For the post-implementation period, the Pathway Platform will be the data source for paired t-test analysis, assessing change in continuous variables including PHQ-9 scores. Categorical outcomes will be presented as proportions and compared using Pearson Chi2 test. Continuous outcomes will be assessed for normality and presented as means and standard deviations (SD) or medians and interquartile ranges (IQR); continuous outcomes will be compared using Student's t test for independent groups. Two-tailed tests using a significance threshold of $p < 0.05$ will be used for all tests.

Exploratory outcomes: will be described among patients attending the pathway platform clinics only and will be compared between baseline, 6-month and extended follow up. Change in these outcomes overtime, including utilization analytics will also be explored. Categorical outcomes will be presented as proportions and compared using McNemars' test. Continuous outcomes will be assessed for normality and presented as means and standard deviations (SD) or medians and interquartile ranges (IQR); continuous outcomes will be compared using Student's Paired t test for single group comparison. Two-tailed tests using a significance threshold of $p < 0.05$ will be used for all tests. Goal attainment will be summarized by proportion of patients who achieve their identified goals based on the set time bound duration of the goal (i.e., GAS Score ≥ 50).^{29,30} The goal attainment scale adapted for depression yields a norm-based score (standardized to a mean of 50, SD of 10) at baseline and at the end of the time bound goal; the change from score from baseline will also be summarized.

System level performance: Process outcomes will be evaluated at the system level (all primary

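### The primary pre/post chi-square ignores clinic, and nothing ties a clinic's share of the pre cohort to its share of the post cohort, so a change in clinic mix is counted as a platform effect.

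*Combined protocol and SAP*

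**What the plan says.** The primary endpoint (section 8.3.1) is binary: "documentation of at least 2 PHQ-9 scores in the EMR over the initial 6-month study period". Section 8.4 states the test, "Categorical outcomes will be presented as proportions and compared using Pearson Chi2 test", and section 8.2 sizes the study "using Pearson chi square test for two independent proportions". No section adjusts this comparison for clinic. Care model appears only as a subgroup factor (section 8.3.3).

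Section 4 wants clinics that are "representative of different geographic locations, patient populations, and care models for depression management, including behavioral health integration models". The two cohorts are then filled by different routes:

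- **Post cohort.** Section 3.1 sets only an overall target, to "enroll a total of 200 patients for six-month duration". Section 4.3 describes how patients arrive: "These patients will be introduced to the study opportunity by care team members during routine clinic visits". Under section 4.4.3, care team members "must complete specific training before they are able to enroll patients".
- **Pre cohort.** Another 200 patients from the same clinics are found through chart reviews and data pulls (Sample Size and Population; section 3.2). The only per-clinic figure is in section 3.2: "Depending on the number of eligible patients identified per site (20 per site), group level matching for age and sex may be conducted".

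**The concern.** Using the same clinics in both periods fixes the list of clinics but not their weights. A clinic with engaged, trained staff may supply many post patients and only an average number of pre patients. If such clinics also recorded PHQ-9 more often beforehand, the pooled post rate rises with no platform effect at all. The reverse pattern hides a real effect.

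The figure of 20 per site does not settle this. Over 20 sites it gives 20 × 20 = 400, the total sample; it gives one cohort of 200 only with 10 sites (10 × 20 = 200). It stands in the pre-cohort section and describes eligible patients. The matching attached to it is optional and covers age and sex, not clinic.

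**Working it through.** **1. The plan's own figure.** Inputs from section 8.2: 75% vs 90%, 80% power, two-sided alpha 0.05, Pearson chi-square. With pooled variance, n = [1.960·√(2·0.825·0.175) + 0.842·√(0.75·0.25 + 0.90·0.10)]² / 0.15² ≈ 99.5, so 100 per group. This reproduces the plan. With the planned 200 per group, power is 97.9% by normal approximation and 98.2% exactly.

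**2. Size of the mix effect.** With two clinic types and no platform effect:

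spurious difference = (high rate − low rate) × (post share − pre share of high-rate clinics).

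The documents give none of these inputs, so all are assumed. Exact rejection rates of the planned chi-square, 200 per group, pre rate 75%:

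| Gap × share difference | Spurious difference | False positives |
|---|---|---|
| 10 × 5 points | 0.5 points | 5.2% |
| 10 × 10 points | 1 point | 5.6% |
| 30 × 5 points | 1.5 points | 6.4% |
| 20 × 10 or 10 × 20 points | 2 points | 7.6% |
| 30 × 10 points | 3 points | 10.9% |
| 20 × 20 points | 4 points | 15.9% |
| 30 × 20 points | 6 points | 30.6% |

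**3. The opposite direction.** At the planned 75% vs 90%, a 4-point shift against the platform leaves an apparent 75% vs 86%, and exact power falls from 98% to 80%. A 6-point shift (75% vs 84%) leaves 61%.

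**4. Stratified against crude, no platform effect.** Simulation with 20,000 runs, clinic types at 90% and 60%, high-type share 50% pre and 70% post:

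| | 20 clinics | 10 clinics |
|---|---|---|
| Crude chi-square | 30.3% | 30.1% |
| Clinic-stratified Cochran-Mantel-Haenszel (CMH) | 5.0% | 4.8% |
| Crude, pre cohort drawn in proportion to post | 3.7% | 3.8% |

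With 20 clinics the mean crude difference is +6.0 points and the stratified one about 0. A separate 40,000-run check on two strata, with the share moving from 50% to 70%, gave crude error of 7.4%, 15.3% and 29.3% for gaps of 10, 20 and 30 points, and 4.8% to 5.0% for CMH.

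**5. Shares that differ without pattern.** Shares drawn independently for each cohort (Dirichlet, concentration 8 per clinic for mild variation and 2 for strong), gaps of 10 to 30 points:

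| Crude error | Mild | Strong |
|---|---|---|
| 20 clinics | 5.3–6.7% | 5.6–12.0% |
| 10 clinics | 5.1–8.6% | 6.4–18.3% |

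CMH stays at 4.7% to 5.2% throughout. With equal shares, the crude test gives 3.6% to 5.0%.

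**6. Power of the stratified test.** With 20 clinics, equal expected shares and stable clinic effects, a 10-point effect gives 71.7% (CMH) vs 71.4% (crude), and 15 points gives 97.5% vs 97.3%. With a true 15 points and the mix against the platform (70% pre, 50% post; types at 83% and 63%), the crude estimate is 11.0 points with 83.7% power. The stratified estimate is 15.0 points with 98.1% power.

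**The case against.** - **20 per site may be a quota.** Ten pre and ten post patients at each of 20 sites also make 400, and then there is no mix bias. The reading is possible, but the text does not state it and sets no per-site number for the post cohort. One clarifying sentence would settle it.
- **The size is assumed.** This stands. The 31% needs a 30-point gap and a 20-point share difference working in the same direction. With a 5-point share difference, error is 5.2% to 6.4%.
- **Clinic gaps may be narrow.** Section 4 limits sites to Epic-integrated clinics and favours high-volume, engaged ones, and eligibility requires a recent or index-visit PHQ. The app also sends biweekly PHQ-9 scores to the record, which may level post rates. The first two could shrink the gap. The third is itself a platform effect, so it does not protect the false-positive rate, which is defined with no such effect.
- **Mantel-Haenszel may target no clear population when effects differ.** Take pre rates of 85% and 65%, 90% post everywhere, and a high-type share of 50% pre and 70% post. The crude difference is 15.0 points, the effect in the post mix is 0.7 × 5 + 0.3 × 25 = 11.0, and Mantel-Haenszel gives 12.8. This stands for stratification alone. Once pre shares equal post shares, Mantel-Haenszel gives 11.0.
- **CMH is worse if clinics change differently.** This also stands. With an assumed SD of 10 points, its error is 8.3% (20 clinics) and 11.5% (10), against 7.5% and 10.3% for the chi-square. The clinic-level analysis in the fix addresses it.
- **Power has slack.** The sample was doubled, so a 4-point adverse shift still leaves 80% at the planned effect. That does not correct the estimate.

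**Conclusion.** The concern holds. The primary test has no clinic stratification, and no stated rule equalises clinic shares between cohorts; both follow directly from the text. The consequence is conditional: clinics must differ in PHQ-9 recording and their shares must differ between cohorts. The plan makes both plausible and controls neither. Under the assumed 10 to 30 point gaps and 10 to 20 point share differences, the bias is 1 to 6 points and the false-positive rate 5.6% to 31%; with similar shares it is negligible. This should be fixed before the chart pull, because the remedy is cheap and the direction of the bias cannot be known in advance.

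**What to change.** 1. **Sampling.** Draw the pre cohort at random within each clinic, in proportion to that clinic's post enrolment. Where a clinic has too few eligible pre patients, take all and rely on stratification. If 20 per site is meant as a quota in both cohorts, say so; that does the same job.
2. **Primary analysis.** Use a clinic-stratified Mantel-Haenszel risk difference with 95% CI and a CMH test, keeping the plain chi-square as supportive. Report any clinic with patients in only one cohort, since it drops out of the estimate.
3. **Sensitivity A.** Fit a linear risk-difference regression on period and clinic indicators, adding age, sex, comorbidity count and qualifying medication event from records before the index visit, with robust errors. Use no covariate for whether a PHQ-9 was recorded and no app-collected PHQ-9 score. Simulated null error is 4.4% (20 clinics) and 4.7% (10).
4. **Sensitivity B.** Give the Mantel-Haenszel estimate with clinic-level errors and t on (clinics − 1) degrees of freedom. When clinics change differently (SD 10 points), its error is 5.3% (20 clinics) and 5.0% (10).
5. **Limits.** State that neither stratification nor adjustment removes consent selection or calendar trend.

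The cost is a sampling rule and a few lines of SAP text, with no extra patients and no power loss for the primary test if clinic effects are stable. Sensitivity B has 96% (20 clinics) or 93% (10) power for 15 points when clinic effects are stable, and wider intervals when clinics change differently.

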8. STATISTICAL CONSIDERATIONS

8.1 General Design and Hypothesis

The following hypotheses will be examined:

Primary hypothesis: PHQ-9 utilization will be greater after implementation compared to before implementation of the Pathway Platform.

Secondary hypothesis: Provider processes and patient depression related outcomes will have greater improvements in patient outcomes after implementation of the App compared to previous practice patterns.

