8.3.2 Secondary outcome

Process outcomes: The following secondary process outcomes will be compared between patients attending clinics pre- and post- implementation of the Pathway Platform.

- Measurement- based care: The proportion of patients reflecting measurement-based care informed MDD treatment adjustments in their charts, defined as at least one dose change, medication switch, or add on medication during the study period. The frequency and types of treatment adjustments will also be explored.
- Shared- decision making: The proportion of patients reflecting shared-decision making, using the OPTION12 Tool framework.²⁶ The tool will be modified by adding a thirteenth domain inquiring about goal setting (Asking the patient or caregiver about goals of treatment). The frequency and domains of shared-decision making will also be explored in a manual chart review and a variable added to assess if the clinician documented asking the patient about their goals of treatment.
- Referrals to behavioral health: The proportion of patients with at least one referral will be compared. The frequency and types of referrals will also be explored.
- Follow-up after hospitalization for mental illness: The proportion of hospitalized adults who receive follow-up within 7 days of discharge and within 30 days of discharge.
- Follow-up after emergency department visit for mental illness: The proportion of adults

who receive follow-up within 7 days of discharge and within 30 days of ED visit.

- Healthcare resource utilization: Number and costs associated with hospital admission, length of stay, emergency room admissions, and encounters with outpatient clinics. Costs will be calculated using USA national average costs for inpatient and outpatient visits or using an average Advocate Health Care system cost.

Patient clinical outcomes: The following outcomes will be compared between patients attending clinics pre- and post- implementation of the Pathway Platform, keeping in mind that the number of patients with these measures in the pre- implementation patient group will be limited:

- MDD remission: The proportion of patients with PHQ-9 ≤ 5 at the end of the study period. The last measurement available during the study period will be used to calculate remission.
- MDD response: The proportion of patients with a 50% or greater reduction in PHQ-9 scores. The first and last scores available during the study period will be used to calculate response.

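### Some 16 to 17 unadjusted pre/post tests serve one broad secondary hypothesis, with no rule for when it is supported and no stated direction of benefit for several outcomes

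*Combined protocol and SAP*

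**What the plan says.** Section 8.1 states its one secondary hypothesis as follows: "Provider processes and patient depression related outcomes will have greater improvements in patient outcomes after implementation of the App compared to previous practice patterns". Section 8.4 makes its outcomes the subject of formal testing: "For primary and secondary hypothesis testing, process measures, patient clinical outcomes, and health care resource utilization will be compared pre- and post- implementation". The threshold follows, and is repeated for the exploratory outcomes: "Two-tailed tests using a significance threshold of $p < 0.05$ will be used for all tests".

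Section 8.3.2 lists the outcomes compared between cohorts:

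- treatment adjustment, "defined as at least one dose change, medication switch, or add on medication during the study period";
- shared decision-making: "The proportion of patients reflecting shared-decision making, using the OPTION12 Tool framework";
- behavioural health referral: "The proportion of patients with at least one referral will be compared";
- follow-up after a mental-health admission: "The proportion of hospitalized adults who receive follow-up within 7 days of discharge and within 30 days of discharge";
- follow-up after an emergency visit, for patients "who receive follow-up within 7 days of discharge and within 30 days of ED visit";
- counts and costs of admissions, emergency visits and outpatient encounters, plus length of stay;
- PHQ-9 remission and PHQ-9 response.

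One further item, the change in diagnosis wording in progress notes, is marked as descriptive. The other between-cohort outcomes carry no such label. PAM-13, CollaboRATE and WSAS are also secondary outcomes, but they are compared over time within platform users only.

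**The concern.** The primary hypothesis rests on one defined endpoint. The secondary hypothesis rests on many, and the plan does not say how many must succeed, or which. A report that followed the plan could present any one significant pre/post comparison as support, and the 0.05 threshold would not describe the error rate of that conclusion.

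Direction adds to the problem. Section 8.1 speaks of improvement in general, but 8.3.2 does not say whether more or fewer referrals, outpatient encounters, admissions or costs would be an improvement. Outpatient encounters are the clearest case: more could mean better engagement or greater burden. For treatment adjustment, the measurement-based-care label implies that more is better, but the plan does not say so. Where direction is open, a significant result either way could be read as success after the data are seen.

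**Working it through.** **The plan's own figure.** The documents state no familywise error rate and no number of secondary tests, so there is nothing to reproduce on this point. The sample size for the primary (8.2) does reproduce. For 75% vs 90%, 80% power and two-sided 0.05, n = [1.960·√(2·0.825·0.175) + 0.842·√(0.75·0.25 + 0.90·0.10)]² / 0.15² = 99.5, so 100 per group. The primary is one test at 0.05 and is not affected by what follows.

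**Count of pre/post tests (8.3.2).**

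| Outcome | Tests | Direction of benefit |
|---|---|---|
| Treatment adjustment | 1 | more is implied |
| Shared decision-making | 1 | more is implied |
| Behavioural health referral | 1 | not stated |
| Follow-up after admission, 7 and 30 days | 2 | more is implied |
| Follow-up after emergency visit, 7 and 30 days | 2 | more is implied |
| Number and cost of admissions, emergency visits and outpatient encounters (6); length of stay (1), with or without its cost (0-1) | 7-8 | not stated |
| Remission, response | 2 | clear |
| **Total** | **16-17** | **8-9 not stated** |

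This assumes one version of each utilisation item. Table 1 in 5.1 collects emergency visits, admissions and outpatient visits both for all causes and for mental illness, and 8.3.2 does not say which is tested, so the count could be higher.

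**Chance of at least one significant result if nothing changed, tests independent.**

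- Either direction counts, 0.05 per test: 1 − 0.95^16 = 56.0%; 1 − 0.95^17 = 58.2%.
- Only favourable results count, 0.025 per test: 1 − 0.975^16 = 33.3%; 1 − 0.975^17 = 35.0%.
- Direction open for referral and all utilisation and cost items, fixed for the rest: 1 − 0.95^8 × 0.975^8 = 45.8% (16 tests); 1 − 0.95^9 × 0.975^8 = 48.5% (17 tests).
- Direction open only for treatment adjustment, referral and the number and cost of outpatient encounters: 1 − 0.95^4 × 0.975^12 = 39.9% (16 tests).

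The expected number of false positives in either direction is 16 × 0.05 = 0.8, or 17 × 0.05 = 0.85.

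**Effect of correlation.** The 7-day measure is nested in the 30-day one, cost largely follows number when average unit costs are used, and remission and response share the last PHQ-9. The documents give no correlations, so the values below are assumptions. They come from simulating 16 equicorrelated normal test statistics (200,000 draws).

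| Common correlation | Either direction | Favourable only |
|---|---|---|
| 0 | 56% | 33% |
| 0.3 | 48% | 25% |
| 0.5 | 37% | 19% |
| 0.7 | 26% | 13% |

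As a cruder check, if the overlaps left about 12 effective tests (also an assumption), the figures would be 1 − 0.95^12 = 46.0% and 1 − 0.975^12 = 26.2%.

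**The case against.** The strongest reply is that 0.05 is a per-test threshold. The plan claims no familywise rate and nowhere says that one significant test is enough. Unadjusted secondary tests beside a single primary are common in a minimal-risk implementation study, and 8.3.2 itself warns that clinical measures in the pre-implementation cohort will be limited. This stands as far as it goes: the one-success reading is an assumption. But the plan does call these comparisons hypothesis testing, and nothing in it excludes that reading. The missing rule is the gap.

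Three stronger readings are tempting, and the documents do not support them.

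- A reader might infer that chance support is more likely than not. That needs worsening to count as support and the tests to be close to independent. Section 8.1 asks for improvement, and with favourable results only the figure is about a third at most.
- A reader might put the count at about 20 by adding PAM-13, CollaboRATE and WSAS. Those compare platform users with themselves, whereas the hypothesis is a comparison with previous practice, so they do not test it.
- A reader might multiply the subgroup factors by the outcomes and reach hundreds of tests. That count cannot be derived. Subgroup analysis sits under the exploratory outcomes (8.3.3), the Appendix 3 comorbidities need not each be a separate factor, and app and report use exist only after implementation, so they cannot define subgroups for a pre/post contrast.

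**Conclusion.** The point holds as a gap in the decision rule: one omnibus hypothesis, 16 to 17 pre/post tests at unadjusted two-sided 0.05, no criterion for support, and no stated direction for 8 to 9 of them. If a single success were taken as support and nothing had changed, the false-positive chance under independence is at most about 56-58% in either direction, about 33-35% if only favourable results count, and about 40-49% with some directions open. Correlation lowers all of these; the smallest case above is 13%. The figures rest on the count of tests, on the one-success reading and on assumed correlations. The primary conclusion is not touched, so this is an inexpensive improvement to the plan and no threat to the trial's main result.

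**What to change.** In 8.1 and 8.4, replace the rule of 0.05 for every test with the following:

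1. Name a short list of key secondary outcomes, for example treatment adjustment, shared decision-making, response and remission.
2. State for each the direction that counts as improvement.
3. If significance is to be claimed, apply Holm's procedure within the list. With four outcomes the ordered p-values are compared with 0.05/4 = 0.0125, 0.05/3 = 0.0167, 0.05/2 = 0.025 and 0.05, which holds the familywise rate at 5%. Unadjusted, four independent tests would give 1 − 0.95^4 = 18.5%.
4. Report all other secondary, exploratory and subgroup results as estimates with 95% confidence intervals, labelled nominal, with no significance claim.

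This needs no new data or patients, only a change of wording. The downside is that some secondary results with p below 0.05 could no longer be claimed as significant.
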